## **9. EFFICACY ANALYSES**

The primary and secondary efficacy analyses will be based on the EE Population. Analyses on the ITT Population will only be performed if greater than 20% of ITT subjects are excluded in the EE Population. All analyses are to be carried out on observed data, as there are no imputations planned. The efficacy data are a result of the centralized, specialized nuclear magnetic resonance (NMR) lipoprotein assay and the central laboratory serum chemistry. All analyses of lipoprotein metabolism will include fasted samples only. For all lipoprotein concentration values, the serum chemistry panel results will be used. For particle size and particle concentration, the NMR lipoprotein assay results will be used. Sensitivity analysis may be performed with the NMR lipoprotein concentration results.

### **9.1. Primary Efficacy Analyses**

The primary efficacy analysis, changes in LDLc, LDLs, and LDLpc at Week 16 (end of DB) from Baseline will be summarized by treatment group, using the EE Population.

The observed values, change from Baseline, and percentage change from Baseline will be summarized by treatment group and visit using arithmetic summary statistics as described in [Section 6.2.1](#).

In order to provide estimates of the change from Baseline and corresponding 95% CI, the ANCOVA methods described in [Section 6.2.3](#) will be applied with change from Baseline as the dependent variable, including treatment group, and randomization stratification factor as fixed effects and Baseline as a covariate. The same analysis will be carried out using percentage change from Baseline as the dependent variable. Model fit will be assessed in order to determine the validity of the estimates. Estimates of LS means, SEs, and 95% CIs will be presented by treatment group.

The comparison of LDLc, LDLs, and LDLpc change from baseline and percentage change from baseline values between each active treatment group and placebo group at each DB post-Baseline visit will be performed as exploratory analyses. Estimates of the LS mean difference

between each active treatment group and placebo group, the SE of the difference, and 95% CI of the difference will be presented.

The relationship of OCA dose level and changes in LDLc will be explored using the Jonckheere-Terpstra (JT) test.

Sensitivity analysis for the primary efficacy analysis will be performed using the ITT Population using both the ANCOVA methods described in [Section 6.2.3](#) and the ANCOVA with repeated measures methods described in [Section 6.2.4](#).

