## 1. INTRODUCTION

This document outlines the statistical methods to be implemented during the analyses of the double-blind (DB) data collected within the scope of Intercept Pharmaceuticals, Inc. (henceforth referred to as Intercept or the Sponsor) for Protocol 747-209 (A Phase 2, Randomized, Double-Blind, Placebo-Controlled Clinical Study Investigating the Effects of Obeticholic Acid and Atorvastatin Treatment on Lipoprotein Metabolism in Subjects with Nonalcoholic Steatohepatitis). The purpose of this statistical analysis plan (SAP) is to provide specific guidelines from which the analyses will proceed. Any deviations from these guidelines will be documented in the clinical study report (CSR). The scope of this plan includes the detailed specifications of the statistical analyses for the DB only. A separate SAP will be written for the long-term safety extension (LTSE) phase of the study. The analyses described in this plan are considered a priori, in that they have been defined prior to database lock of the DB. Post hoc analyses will be labeled as such on the outputs and identified in the CSR. Further details about study design and procedures can be found in the protocol.

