## 2. STUDY OBJECTIVES

The DB primary objective is to evaluate the effect of obeticholic acid (OCA) on low-density lipoprotein (LDL) metabolism in subjects with biopsy-confirmed nonalcoholic steatohepatitis (NASH) and to assess the ability of atorvastatin to modulate this effect.

The DB secondary objectives are:

- To evaluate the safety and tolerability of OCA alone and in combination with atorvastatin therapy in subjects with biopsy-confirmed NASH.
- To evaluate the effect of OCA with and without atorvastatin therapy, on
  - High-density lipoprotein (HDL), very low-density lipoprotein (VLDL), triglycerides (TG), total cholesterol, and apolipoprotein (Apo) concentrations
  - Components of the reverse cholesterol transport pathway

The DB exploratory objectives are:

- To evaluate the effect of OCA on:
  - Liver biochemistry, inflammation, and apoptosis
  - Markers of glucose metabolism including C-peptide, insulin, fasting plasma glucose, hemoglobin-specific A1c fraction (HbA1c), homeostatic model assessment – beta-cell function (HOMA- $\beta$ ), and homeostatic model assessment – insulin resistance (HOMA-IR)
  - Anthropometric measures including height (measured at Screening Visit 1 only), weight, waist and hip circumference measurements, body mass index (BMI), and waist-to-hip ratio calculations
  - Cardiovascular risk scores (eg, Framingham Risk Score [FRS] and Reynolds score)

- To evaluate the pharmacokinetics (PK) and pharmacodynamics (PD) of OCA and its conjugates
- To evaluate the bioanalytical concentrations of atorvastatin and its metabolites
- To evaluate improvement in noninvasive-radiological assessment of fibrosis via transient elastography (TE; at sites where available)

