### **3. STUDY ENDPOINTS**

#### **3.1. Primary Endpoints**

The DB primary endpoints are change and percentage change from Baseline to Week 16 in LDL cholesterol concentration (LDLc), particle size (LDLs), and particle concentration (LDLpc).

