## **4. STUDY DESIGN AND PLAN**

This is a Phase 2, double-blind, randomized, placebo-controlled, multicenter study, evaluating the effects of OCA, and the subsequent addition of statin therapy, on lipoprotein metabolism in subjects with NASH with fibrosis stage 1 to 4, but no evidence of hepatic decompensation, in the DB phase, followed by an open-label LTSE phase to evaluate long term safety and efficacy.

Approximately 80 subjects with histological evidence of definite or probable NASH, who meet all inclusion and none of the exclusion criteria will be enrolled in the study. The histological evidence of definite or probable NASH will be based on the central read of a liver biopsy obtained no more than 1 year prior to randomization and a nonalcoholic fatty liver disease activity score (NAS) of 4 or greater. Subjects not using statin therapy (ie, statin-free) and statin-treated subjects may be enrolled. Statin-treated subjects will be required to stop statin treatment (after signing informed consent) for up to 5 weeks, including a 4-week statin washout period, prior to Randomization/Day 1.

Subjects will have a screening period of up to 5 weeks prior to Randomization/Day 1. At the Randomization (Day 1) Visit, subjects will be randomized in a 1:1:1:1 ratio to receive OCA 5 mg, OCA 10 mg, OCA 25 mg, or placebo, orally, once daily, for 16 weeks. Randomization will be stratified by the pre-randomization fasting serum LDLc ( $\leq$ 125 mg/dL or  $>$ 125 mg/dL) and baseline fibrosis stage (stage 1, 2 or stage 3, 4).

[figure not shown]
Subjects will attend on-site clinic visits at Weeks 2, 4, 8, 12, and 16 and will be contacted at Weeks 6, 10 and 14 to assess safety and treatment compliance. At the Week 4 Visit, all subjects will initiate treatment with atorvastatin at a dose of 10 mg once daily. At the Week 8 Visit, atorvastatin will be increased to 20 mg once daily (if 10 mg daily is tolerated), and continued for an additional 4 weeks. After 4 weeks of treatment at 20 mg, the atorvastatin dose may be titrated (up or down) as clinically indicated. The final visit during the DB phase will occur at Week 16, after which subjects may continue into the open-label LTSE.

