## 5. DETERMINATION OF SAMPLE SIZE

It is the intent of this study to characterize the components of LDL metabolism (ie, LDLc, LDLs, and LDLpc) in subjects with NASH before and after treatment with OCA and to assess the changes induced by HMG Coenzyme A reductase inhibitor (atorvastatin) therapy. Assuming a 22 mg/dL increase from Baseline with a standard deviation of 24 in LDLc in the OCA 25 mg group without atorvastatin therapy after 16 weeks of treatment based on data from FXR Ligand OCA in NASH Treatment (FLINT) study, a sample size of 20 subjects per group will provide greater than 97.3% power to demonstrate the statistically significant difference of LDLc increase from Baseline with a 2-sided type I error of 0.05.

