### 6.2.3. Analysis of Covariance

Analysis of covariance (ANCOVA) will be performed to provide least squares (LS) mean estimates and 95% confidence intervals (CIs) of the change and percentage change from Baseline at each DB post-Baseline visit. Model covariates will include the randomization stratification values (ie, pre-randomization fasted serum LDLc [ $\leq 125$  mg/dL or  $> 125$  mg/dL] and baseline fibrosis stage [stage 1, 2 or stage 3, 4]) and the Baseline value of the parameter being evaluated. The primary analysis will exclude the treatment by visit interaction term.

Example SAS code for the primary analysis is as follows:

ODS graphics on;

```
proc mixed data=ADEFF noclprint plots=residualpanel;
```

```
by visit;
```

```
class ldlcon fbstg trt;
```

```
model change=Baseline ldlcon fbstg trt / ddfm=kr;
```

```
lsmeans trt / cl diff alpha=0.05;
```

```
title1 "Linear Mixed Effects Model Based Estimates of XXXX Means by Visit";
```

```
title2 " Fixed Effects for Visit, Randomization Strata and Baseline as Covariates";
```

```
run;
```

```
ODS graphics off;
```

```
quit;
```

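### The primary within-arm Week 16 LDL change is a net effect of OCA, atorvastatin and time, and Section 5's 97.3% power is not the power for it

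*SAP*

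**What the plan says.** - **Objective (Section 2).** The primary objective is the effect of OCA on LDL metabolism and, secondly, "to assess the ability of atorvastatin to modulate this effect".
- **Endpoint (Section 3.1).** The primary endpoints are "change and percentage change from Baseline to Week 16 in LDL cholesterol concentration", together with LDL particle size and particle concentration.
- **Design (Section 4).** Four arms are randomized 1:1:1:1. "At the Week 4 Visit, all subjects will initiate treatment with atorvastatin at a dose of 10 mg once daily". The dose goes to 20 mg at Week 8 if tolerated, and may be titrated individually after four weeks at 20 mg.
- **Sample size (Section 5).** The aim is to characterize LDL metabolism "before and after treatment with OCA and to assess the changes induced by HMG Coenzyme A reductase inhibitor (atorvastatin) therapy". Power above 97.3% is stated for a rise of 22 mg/dL, SD 24, "in the OCA 25 mg group without atorvastatin therapy after 16 weeks of treatment", with 20 subjects per group and two-sided 0.05.
- **Primary analysis (Section 9.1).** "The primary efficacy analysis, changes in LDLc, LDLs, and LDLpc at Week 16 (end of DB) from Baseline will be summarized by treatment group", in the EE Population, with per-arm LS means, SEs and 95% CIs. OCA-minus-placebo LS mean differences with SE and 95% CI are planned at every post-Baseline visit and called exploratory. The Section 6.2.3 code already produces them: "lsmeans trt / cl diff alpha=0.05".
- **Inference (Section 6.2.8).** The study is descriptive, without multiplicity adjustment.
- **ITT (Sections 9 and 9.1).** Section 9 allows ITT analyses only if more than 20% of ITT subjects are excluded from EE. Section 9.1 plans ITT ANCOVA and repeated-measures analyses of the primary endpoints with no such condition.

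**The concern.** By Week 16 every arm has been scheduled for 12 weeks of atorvastatin. A per-arm Baseline-to-Week 16 change therefore adds together whatever OCA does, whatever atorvastatin does and any drift over time. It fits the before-and-after aim of Section 5. It does not answer the first half of the primary objective, because the same OCA effect can show as a rise, no change or a fall depending on how much atorvastatin lowers LDLc.

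The stated power has a related fault. A reader would attach 97.3% to the Week 16 primary endpoint, or to OCA versus placebo, and it describes neither.

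The ITT rule is a separate matter. Two instructions in the same plan give different answers on whether the ITT analyses of the primary endpoints are run.

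At stake are which estimate the report offers as the OCA effect, what precision the study is said to have, and which ITT tables are produced.

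**Working it through.** **Inputs from the SAP.** Change +22 mg/dL, SD 24, n = 20 per group, two-sided 0.05 (Section 5); atorvastatin in all arms from Week 4 (Section 4); 20% EE threshold (Sections 7.4 and 9). The SAP gives no placebo change, no atorvastatin effect and no OCA-placebo difference, so these are assumed below and shown as ranges.

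**1. Reproduce the stated power.** One-sample t-test on change, noncentral t with 19 df:
- noncentrality = 22/24 × √20 = 4.10; power = 97.29%, which rounds to the stated 97.3%.

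Two-sample t-test, OCA 25 mg versus placebo, same inputs, 38 df:
- noncentrality = 22 / (24 × √(2/20)) = 2.90; power = 80.6% (82.6% by normal approximation).

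The stated figure is therefore a single-arm calculation. Its arithmetic is right. What does not fit is the condition it describes, since under Section 4 OCA without atorvastatin is scheduled only up to Week 4.

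**2. What the within-arm change shows at Week 16.** Assume atorvastatin lowers LDLc by A mg/dL, additive to the +22, SD still 24, n = 20. Net change = 22 − A.

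| A (assumed) | Net change | One-sample power |
|---|---|---|
| 0 | +22 | 97.3% |
| 10 | +12 | 56.5% |
| 15 | +7 | 23.6% |
| 22 | 0 | 5.0% |
| 30 | −8 | 29.4% (for a fall) |
| 40 | −18 | 88.9% (for a fall) |

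If A is equal in both arms, it cancels from the OCA-placebo difference.

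**3. Precision and power for OCA 25 mg versus placebo, SD 24.**
- 20 per arm: half-width = t(0.975, 38) × 24 × √(2/20) = 15.4 mg/dL.
- 16 per arm (assumed 20% lost to EE): t(0.975, 30) × 24 × √(2/16) = 17.3 mg/dL.
- Power at 20 per arm by assumed true difference: 80.6% for 22, 58.8% for 17, 48.7% for 15, 25.0% for 10.
- Power at 16 per arm for 22: 70.9%.
- Power at 20 per arm for 22 with SD 30: 61.8%.

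A difference of 22 equals Section 5's single-arm change only if the placebo change, net of atorvastatin, is zero.

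**4. Modulation by atorvastatin.** Section 6.2.3 runs `by visit`. The pairwise `diff` on `trt*week` in Section 6.2.4 gives each arm's own Week 16 minus Week 4 difference with a CI, but no contrast of those differences between OCA and placebo. Such a contrast would have SD of change = 24 × √(2(1−ρ)) = 28.4, 24.0 and 18.6 for assumed ρ of 0.3, 0.5 and 0.7. Half-widths at 20 per arm are 18.2, 15.4 and 11.9 mg/dL. With an OCA effect of 22 at both visits, the contrast is 0 if atorvastatin acts additively. If atorvastatin lowers each value by a proportion p, it is −22p, that is −2.2 to −8.8 mg/dL for falls of 10 to 40%.

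**5. ITT instructions side by side.**
- Section 9: ITT only if more than 20% of ITT subjects are excluded from EE.
- Section 9.1: ITT ANCOVA and repeated-measures sensitivity analyses, unconditional.
- Section 9.3.4: stiffness-biopsy correlation on ITT, unconditional.
- Appendix A, all without condition: LDL on ITT (14.2.1.2.1-3 and 14.2.1.3.1-3), LDL change by treatment on ITT (14.2.1.4.1-2), HDL MMRM on ITT (14.2.2.2.1-3), VLDL MMRM on ITT (14.2.3.2.1-2).
- Appendix A writes out the 20% condition for table 14.1.4.3, so it marks conditional tables at least there.

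**The case against.** The strongest reply is that little changes in what is computed. The study is declared descriptive, the OCA-placebo differences with SE and CI are planned at every visit, and Section 3.1 defines an endpoint rather than a within-arm contrast. The ranking may come from the protocol, which is not at hand. All of that stands, and it keeps the point to one of labelling, precision and consistency.

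Four stronger readings are tempting, and the SAP does not support them.

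- *The plan cannot estimate the OCA effect, or will report the within-arm change as that effect.* The randomized differences are planned, and no section says the within-arm change will be so read.
- *The OCA-placebo differences isolate OCA.* At Week 16 they estimate OCA on background atorvastatin, whose dose may differ by arm after individual titration. In EE they are also conditioned on completing the double-blind phase at the indicated doses without major deviations, which is settled after randomization. That applies to the Week 4 difference too when it is taken in EE. The Week 4 difference covers only four weeks of OCA.
- *The true power is about 81%.* That needs a difference of 22, hence zero placebo change net of atorvastatin, with SD 24 holding on atorvastatin. The SAP gives neither.
- *The modulation objective has no estimate at all.* The arm-specific Week 16 minus Week 4 changes come from the Section 6.2.4 model with CIs, and the between-arm point estimate follows by subtraction. What is missing is an interval for it, and that interval would be wide.

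**Conclusion.** The point holds, and it should be fixed before database lock.

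- The within-arm Week 16 change describes net change on OCA plus atorvastatin plus time. For an assumed additive atorvastatin fall of 10 to 40 mg/dL, the same OCA effect of +22 appears as anything from +12 to −18.
- The planned OCA-placebo differences are the estimates that address the OCA effect, subject to the titration and EE limits above, and they are ranked below it.
- The 97.3% is a correct one-sample figure for a condition scheduled in no arm at Week 16. For OCA 25 mg versus placebo the supportable statement is a half-width of about 15.4 mg/dL at 20 per arm if SD is 24. Power ranges from 80.6% down to 25.0% for assumed differences of 22 down to 10.
- The ITT sentence in Section 9 conflicts with Sections 9.1 and 9.3.4 and with Appendix A.

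No type I error claim is at risk, because the plan makes none.

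**What to change.** 1. **Section 5.** Label 97.3% as a one-sample within-arm calculation without atorvastatin that does not apply to Week 16. Add the OCA 25 mg versus placebo half-width (about 15.4 mg/dL at 20 per arm, SD 24). If a power is quoted, give the range with its assumptions: 80.6%, 58.8%, 48.7% and 25.0% for differences of 22, 17, 15 and 10, and 70.9% for 22 with 16 per arm. State that 22 assumes zero placebo change net of atorvastatin.
2. **Section 9.1.** Present the planned OCA-placebo differences at Week 4 (before scheduled atorvastatin, four weeks of OCA) and Week 16 (OCA on background atorvastatin) as the estimates that address the OCA effect, in both ITT and EE. State that atorvastatin dose may differ by arm and that EE is selected after randomization. Keep the within-arm changes as the description of net change.
3. **Section 12.** If the protocol ranks the estimates differently, record the reordering there with its date. Section 1 rests the a priori status of the analyses on the fact that "they have been defined prior to database lock of the DB", and Section 12 shows that some assay results were already known, so the date matters.
4. **Section 6.2.4 (optional).** Add one supportive contrast per dose, (OCA Week 16 − OCA Week 4) − (placebo Week 16 − placebo Week 4), with a 95% CI. Note its low precision and that it also contains any OCA effect developing after Week 4.
5. **Section 9.** Reword the ITT sentence so that every ITT analysis planned without condition always runs: LDL ANCOVA and MMRM, tables 14.2.1.4.1-2, the HDL and VLDL MMRM tables, and the stiffness correlation. The 20% rule then governs only the repeat of the remaining efficacy analyses.

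**Cost.** Mostly wording, with at most one extra row per dose and no new data. The price is a less flattering statement of power and a documented change in the order of the estimates.

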## **9.2. Secondary Efficacy Analyses**

The secondary efficacy parameters will be analyzed in the same manner as the primary efficacy variables. Descriptive statistics will be generated and will include change from Baseline, percentage change from Baseline at each DB post-Baseline visit, and estimates of LS means, SEs, and 95% CIs presented by treatment group.

### **9.2.1. Lipoprotein Metabolism**

The secondary parameters related to lipoprotein metabolism include HDLc, HDLs, HDLpc, VLDLc, VLDLs, VLDLpc, TG, and total cholesterol concentrations; and ApoA1, ApoB, ApoE, ApoCII, ApoCIII, Lp(a), and PCSK9 concentrations.

### **9.2.2. Reverse Cholesterol Metabolism**

The secondary parameters related to reverse cholesterol metabolism include pre- $\beta$ 1 HDL concentration, macrophage cholesterol efflux, LCAT activity, and CETP activity.

## **9.3. Exploratory Efficacy Analyses**

### **9.3.1. Liver Biochemistry and Markers of Liver Function**

The following laboratory parameters will be summarized by treatment group: albumin, ALP, ALT (isoenzymes), AST, direct bilirubin, GGT, INR, total bilirubin, and platelets.

Analyses of observed laboratory values will be carried out using a repeated measures ANCOVA model with change from Baseline as the dependent variable, including treatment group, and randomization stratification factors as fixed effects and Baseline as a covariate as described in [Section 6.2.3](#). The same analysis will be carried out using percentage change from Baseline as the dependent variable.

Arithmetic summary statistics as described in [Section 6.2.1](#) will be used to summarize the laboratory values by treatment group and visit. The results, change from baseline, and percentage change from baseline, as well as estimates of LS means, SEs, and 95% CIs, will be presented by treatment group. Estimates of the mean difference between each active treatment group and placebo group, the SE of the difference, and 95% CI of the difference will be presented.

### **9.3.2. Markers of Liver Inflammation, Hepatic Apoptosis, and Fibrosis**

Markers of liver inflammation, hepatic apoptosis and/or fibrosis include IL-6, hs-CRP, TNF- $\alpha$ , CK-18-M30, and CK-18-M65. These biomarkers will be summarized by treatment group using arithmetic summary statistics as described in [Section 6.2.1](#) at Baseline and at each DB post-Baseline visit. The absolute and percentage change from Baseline will be analyzed using the Wilcoxon Rank Sum Test to compare active treatment groups and placebo. The median differences and 95% CI of the median differences between treatment groups will be constructed using a Hodges-Lehmann estimate as described in [Section 6.2.5](#). The protocol specifies the Sign Test may be used when the median differences between treatments are not symmetrical around the median. The median differences between treatments will always be symmetrical, therefore, the Sign Test will not be used.

### **9.3.3. Glycemic Control**

Glycemic control measures include fasting glucose, fasting insulin, C-peptide, HbA1c, HOMA- $\beta$ , and HOMA-IR. These measures will be summarized using arithmetic summary statistics as described in Section 6.2.1 at Baseline and at each DB post-Baseline visit by treatment group. The change from Baseline will also be summarized. Baseline is defined as the last fasting assessment prior to the administration time of the first OCA dose. Treatment groups will be compared using an ANCOVA model with change from Baseline as the dependent variable, including treatment group, and randomization stratification factors as fixed effects and Baseline as a covariate as described in [Section 6.2.3](#). The same analysis will be carried out using percentage change from Baseline as the dependent variable. Estimates of LS means, SEs, and 95% CIs will be presented by treatment group. Estimates of the mean difference between each active treatment group and placebo group, the SE of the difference, and 95% CI of the difference will be presented. The distribution of glycemic control measures will be evaluated for normality assumptions. If normality assumptions are violated, non-parametric methods, such as a rank ANCOVA model, will be used.

Subgroup analyses will also be presented by diabetes status, excluding the randomization stratification factors from the ANCOVA model.

